The primary outcome measure will be postoperative visual analog pain scale (VAS) score area under the curve (AUC) for 48 hours, recorded every six hours. Pain will be measured indirectly via total in-hospital opioid consumption. Functional outcome measures will be administered by members of the physical and occupational therapy team, who typically evaluate and treat patients once on the day of surgery and twice daily each day thereafter. They will document the patient's ability to perform independent terminal knee extension and grade knee buckling with ambulation on a scale of 0-2 during each encounter. Additionally, in the morning of postoperative day #1, a Katz Index of Independence in Activities of Daily Living score will be calculated. On the morning of postoperative day #2, the therapist will document distance walked by the patient, passive range of motion (flexion and extension), a timed up-and-go test (TUG), and calculate the AM-PAC (Activity Measure for Post-Acute Care) score. Patient reported outcome measures, specifically SF-12, PROMIS, and KOOS will be collected at 6 weeks and 3 months postoperatively. These time points are not included in the FORCE-TJR registry, and therefore will be independently collected and stored. Postoperative complications will be recorded. Finally, a brief survey will be administered at 3 months, presenting inquiries regarding satisfaction with the hospital stay, pain control, mobility, and the overall TKA experience. These inquiries will pose each question with a 0-10 scale, and respondents will be asked to select the number that corresponds to their level of satisfaction with each domain of their experience.

Via partnership with the FORCE-TJR, collection of patient-reported outcomes (PRO) data for arthroplasty patients at MUSC is both well-established and sophisticated. These data will be available as baseline measures for this project. Preoperative data are collected at a mandatory appointment 2-3 weeks in advance of elective arthroplasty. At that appointment and again at follow-up, our research coordinator facilitates patient recruitment and participation with the FORCE-TJR using validated computerized survey

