instruments. Additionally, for this study, she will assist with enrollment, consent, extraction of clinical data from the EPIC-EMR, and coordination of prescribed follow-up. Postoperative SF-12, PROMIS, and KOOS are collected at 6 months and 1 year via the FORCE-TJR, therefore the coordinator will additionally facilitate collection of these instruments at 6 and 12 weeks, as well as the satisfaction survey. If, in the surgeon's opinion, the patient is doing well after surgery and does not have to return to clinic at the specified time points, the surveys will be mailed to the patient with instructions on how to complete them. The study coordinator will be available to field study-related patient questions in clinic and via telephone.

At three months, a random subset of four patients from each randomization arm will be invited to participate in a focus group. The purpose of the focus group will be to facilitate patient engagement with the hope of fulfilling our primary aim of this study, which is to identify the most meaningful outcome measures for perioperative analgesia among the TKA patients themselves. Qualitative data obtained during the recorded session will prompt discussion related to the overall patient experience in addition to individual experiences related specifically to analgesia, postoperative mobility, transitioning to the out-patient setting, and involvement in a randomized trial. The focus group will be held several months after surgery, on the MUSC campus in a private room. Audiotape of the focus group will be available to relevant study personnel only, and will be kept under lock and key within an office in the Department of Orthopaedics. A preference survey will be developed and distributed for additional patient feedback.

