Though the main goal of conducting this pilot study is one of establishing the appropriate data points and testing the feasibility of such a design, we will conduct some preliminary hypothesis testing. Tests on the effect of treatment upon outcomes will be performed using an intent-to-treat analysis. Preliminary estimates suggest the study will be adequately powered to detect a significant VAS difference of 2 at 25 subjects per group. However, prior research suggests that the anticipated group differences may be much subtler, requiring a very large sample size to thoroughly address the issue of which treatment is superior to the others. As a preliminary step towards a larger, more definitive comparative effectiveness trial, we plan to enroll approximately 90 patients. This will allow us to reach our randomization goal of at least 75 patients while taking into account withdrawals. The 75 patients will be randomized into the three treatment arms over a 6-month recruitment period, with a 3 month follow-up for patient reported outcome and satisfaction data. This sample will allow us to estimate means relatively precisely, with 95% confidence intervals extending just 0.4 standard deviation units in either direction. We will also be able to make preliminary estimates of each treatment's effectiveness on the various outcomes of interest. Such estimates can be made using generalized linear mixed models (GLMMs)(6). Effect sizes will then be estimated from the GLMMs in a pairwise manner, and this information will be extremely valuable for use in designing a larger, more definitive trial in the future.

The study timeline calls for initiation in April of 2015, and completion of enrollment in October, 2015. Three-month follow-up data will be collected by the end of January, 2016, which will allow for data analysis and interpretation in advance of PCORI Letter of Intent, anticipated to be due in spring of 2016.

We expect to demonstrate sound scientific methodology and a fully invested multi-disciplinary team that will define clinically meaningful though perhaps not statistically significant differences in efficacy, safety, patient-reported and objective outcomes associated with various strategies of perioperative TKA pain management. With continued

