#### b. Protection against Risk

Risks of data breach and breach of confidentiality exist for participants in this study. In order to minimize such risks, data will be stored in a password-protected, MUSC network drive, and unlinked to personal identifiers other than medical record number. Only study investigators will have access to these data.

In the event of adverse effects to the subjects, necessary medical intervention will be provided in the routine manner. There will be no deviation from the routine postoperative protocol for a total knee replacement other than collection of additional data points mentioned earlier in this proposal.

Adverse events and complications will be recorded and monitored as a part of the study protocol. Any trend suggesting an association between treatment and adverse events will be noted, and study investigators will have the ability to stop randomization into any treatment arm seemingly associated with increased rates of adverse events at their discretion. Any such occurrence will be reported to the IRB.

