### 4. IMPORTANCE OF THE KNOWLEDGE TO BE GAINED

We expect to demonstrate sound scientific methodology and a fully invested multi-disciplinary team that will define clinically meaningful though perhaps not statistically significant differences in efficacy, safety, patient-reported and objective outcomes

associated with various strategies of perioperative TKA pain management. With continued patient engagement, this pilot study will support development of a multi-center randomized comparative effectiveness trial that we expect will be strongly considered for extramural funding through the Patient Centered Outcomes Research Institute (PCORI) via the "Large Pragmatic Studies to Evaluate Patient-Centered Outcomes" Funding Announcement. As a proposed randomized trial examining a poorly defined aspect of treatment that could affect nearly one million Americans per year, such a proposal meets the stated objectives outlined in the RFA. This pilot study will allow us to present a well-formulated, novel, scientific protocol supported by experience and data. Furthermore, it will allow us to demonstrate commitment and capacity for patient engagement in the study design process. The ultimate goal after procurement of extramural funding is to expand and establish this methodology as the generalizable gold standard for comparative effectiveness studies assessing perioperative TKA analgesia, and foster the development of a healthcare learning environment capable of identifying the most optimal strategy for perioperative TKA analgesia. Identification and establishment of a new "gold standard" in perioperative analgesia for TKA patients has the potential to positively impact the perioperative experience and clinical outcomes for nearly 1 million Americans annually.

Each of the proposed treatments are currently commonly used in centers nationwide. There are no reports in the literature that we are aware of suggesting that any of the proposed treatments are associated with increased risk, and all are well-accepted as safe options for perioperative analgesia following total knee surgery. The safety and efficacy of each relative to the others is unknown.

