#### 5. SUBJECT SAFETY AND MINIMIZING RISKS (Data and Safety Monitoring Plan)

Complications thought to be directly related to the treatment will be assessed and documented at each patient encounter during and beyond the study period, beginning with the inpatient hospital stay, and continuing with the 3 week, 6 week, 3 month, 6 month and annual follow up visits. Such complications will include paresthesias, dysesthesias, motor weakness, neuroma, persistent pain, patient falls, and hematoma. Other serious adverse events that may be observed following total knee arthroplasty, but thought to be unrelated to the peripheral nerve block will also be noted. Such events might include wound infections, venous thromboembolic events, and cardiac events, among others. Individual surgeons will be responsible for such monitoring, and all adverse events and complications will be reported to the PI.

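### Late block complications are not actively sought at 6 weeks and 3 months in patients whose clinic return the surgeon waives

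*Protocol*

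**What the plan says.** Protocol Section D sets patient-reported outcomes at 6 weeks and 3 months and a satisfaction survey at 3 months. It then allows the clinic return to be dropped: if the surgeon's view is that "the patient is doing well after surgery and does not have to return to clinic at the specified time points, the surveys will be mailed" with instructions. Nothing else is put in place of the visit. On complications, the outcome paragraph of Section D says only "Postoperative complications will be recorded".

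Section E.5 is more specific. Complications attributed to the block "will be assessed and documented at each patient encounter during and beyond the study period", starting in hospital and "continuing with the 3 week, 6 week, 3 month, 6 month and annual follow up visits". The list covers paresthesias, dysesthesias, motor weakness, neuroma, persistent pain, falls and hematoma. On responsibility it states: "Individual surgeons will be responsible for such monitoring, and all adverse events and complications will be reported to the PI".

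Two uses of these data are announced. Sections D and E.4 expect to define "clinically meaningful though perhaps not statistically significant differences in efficacy, safety, patient-reported and objective outcomes", and E.4 adds: "The safety and efficacy of each relative to the others is unknown". Section E.2.b lets the investigators "stop randomization into any treatment arm seemingly associated with increased rates of adverse events at their discretion".

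**The concern.** Section E.5 ties the assessment of complications to encounters. Section D lets the surgeon remove two of the named encounters, and the ground for removal is how well the patient appears to be doing after randomisation. The surgeon who grants the waiver is also the person responsible for monitoring. For a waived patient the plan sets no complication assessment between 3 weeks and 6 months, and an empty complication record at 6 weeks or 3 months may mean either that there was no event or that nobody asked.

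What is at stake is the description of late safety and the complication rates carried forward to the larger trial. This is a matter of data collection, and an analysis plan cannot recover answers that were never sought.

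**Working it through.** **Is there another route?** The protocol states no figure to reproduce, so the first step is to set the relevant statements side by side.

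| Possible route at a waived visit | What the protocol says | Does it fill the gap? |
|---|---|---|
| Mailed surveys (D) | SF-12, PROMIS, KOOS; 0-10 satisfaction items at 3 months | No complication item is described. Satisfaction with pain control is asked, but no use of the answers to identify complications is stated |
| Telephone (D) | The coordinator answers patients' questions | Patient-initiated; not a scheduled check |
| Record extraction (D) | General coordinator duty | Not tied to complications; without an encounter there is no scheduled assessment to extract |
| General statements (D, E.1.b, E.2.b) | Complications are recorded and monitored | No method given |
| Other visits (E.5) | Inpatient, 3 weeks, 6 months, annual | They cover other times; a 6-month visit may find what persists |

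No stated route covers a waived 6-week or 3-month visit.

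**How large could it be?** The protocol gives no waiver share and no numerical complication rate. Section E.1.c describes the more serious nerve complications as extremely rare. Every input below except the 25 per arm and 75 in total is therefore an assumption.

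Let R be the true rate of complications first appearing or persisting after 3 weeks, k the share waived, f the event rate in waived patients relative to those seen, and d the share of waived patients' events found by other routes.

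- Rate in those seen: rs = R / ((1 − k) + k·f)
- Recorded rate: (1 − k)·rs + k·rs·f·d

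*Equal waiver shares, pessimistic case* (k = 0.30 in all arms, f = 1, d = 0). Missed among 75 = 75 × R × 0.30:
- R = 1%: 0.225 of 0.75 expected events
- R = 10%: 2.25 of 7.5 expected events

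There is no between-arm gap in this case. Per arm of 25 the loss is 0.075 or 0.75 events.

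*Unequal waiver shares*. Gap in recorded events per 25 patients when the true rates are equal:

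| k in the two arms | f, d | R = 1% | R = 10% |
|---|---|---|---|
| 25% vs 35% | 1, 0 | 0.025 | 0.25 |
| 15% vs 45% | 1, 0 | 0.075 | 0.75 |
| 15% vs 45% | 0.5, 0.5 | 0.026 | 0.26 |

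For example, with R = 1%, f = 0.5 and d = 0.5:
- k = 0.15: rs = 0.01/0.925 = 1.081%; recorded 0.85 × 1.081% + 0.15 × 1.081% × 0.25 = 0.959%
- k = 0.45: rs = 0.01/0.775 = 1.290%; recorded 0.55 × 1.290% + 0.45 × 1.290% × 0.25 = 0.855%
- The difference times 25 is 0.026 events

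The 10% column and the 15% versus 45% split are outer limits without support in the protocol. Events already recorded in hospital or at 3 weeks do not belong in R. In the most extreme corner (R = 10%, 45% waived, nothing found otherwise) a single arm would lose 25 × 0.10 × 0.45 = 1.1 events.

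**Bearing on stopping an arm.** Recruitment lasts 6 months. With even accrual (assumed), 3/6 = one half of the 3-month assessments and 1.5/6 = one quarter of the 6-week assessments fall after recruitment has closed. These could not inform a decision to stop randomisation even if every visit took place.

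**The case against.** The strongest reply is that E.5 already fixes who monitors, what, when and to whom it is reported, so that handling a missed visit is an operational detail. In addition, a waiver needs two conditions, doing well and not having to return, and a patient with known weakness or numbness is unlikely to meet both. Inpatient and 3-week assessments come before the gap and 6-month and annual visits follow it. A chart shows whether a patient was seen. Section E.3 reports that the literature suggests equivalent risks across the arms. A self-report checklist does not equal an examination, and it adds burden in a pilot that aims for easy integration into routine work.

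Much of this stands, and it limits the size of the point. It does not remove it. The waiver is a stated rule, and following it yields weaker safety data at two named time points. The later visits help only in part. Section D has three-month data complete by the end of January 2016, ahead of the spring funding application. Patients operated on after July 2015 reach 6 months later than that; with even accrual from April to October they are roughly a third to a half of the sample.

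A reader might infer more than the protocol supports:
- *That Sections D and E.5 contradict each other.* They do not. E.5 ties assessment to encounters, so without an encounter none is due. The two sections are unreconciled.
- *That the comparison of safety between arms is biased.* Nothing shows that waiver shares would differ by arm, and no direction of bias can be given.
- *That the discretion to stop an arm is undermined.* The bearing is limited, because many of these assessments come after recruitment closes and the inpatient and 3-week data remain.

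**Conclusion.** The point holds as a gap in ascertainment with a modest expected effect. At 6 weeks and 3 months, late complications in waived patients are not actively sought, and who is assessed depends on a post-randomisation judgement of outcome. The consequence to expect is some under-counting in the safety description. Distortion between arms is possible only if waiver shares differ.

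The size is not derivable from the protocol. If late complications occur at a rate nearer 1% than 10%, the effect is well under one event per arm, and every between-arm gap in the scenarios above is below one event. The 48-hour VAS outcome, the in-hospital measures, and the inpatient and 3-week safety data are untouched. The change is worth making because it is cheap and because information not asked for at the time cannot be recovered later.

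**What to change.** Reconcile Sections D and E.5 by stating how complications are ascertained when a visit is waived. Give every patient, seen or not, the same short checklist at 6 weeks and 3 months, covering the E.5 complications that a patient can report: numbness or tingling, weakness, falls, persistent pain, and bleeding or swelling. It can go in the survey pack or be asked by call from the existing coordinator. Record whether a visit took place, so that no event reported can be told from not assessed.

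The visit schedule and the mailing option stay as they are. The cost is one extra page or call per patient at two time points and a slight added burden. Some patients will not respond, and self-report does not replace a surgeon's examination.

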of perioperative analgesia for TKA patients, we do expect to produce clinically meaningful, if not statistically significant findings. We expect the study to be adequately powered to establish estimates of variance that will help refine subsequent power analyses for outcome measures that may not yet have precedence in the literature.

At the conclusion of this pilot study, we hope to have compiled valuable experience and knowledge, established collegial relationships across a number of disciplines, and effected a mechanism of meaningful patient engagement in design of a study that will be well-positioned to compete for the expected Patient-Centered Outcomes Research Institute (PCORI) funding via the Large Pragmatic Studies to Evaluate Patient—Centered Outcomes opportunity in the Spring of 2016

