## **D. RESEARCH DESIGN AND METHODS (including data analysis)**

---

All **primary** TKA patients undergoing surgery at the Medical University of South Carolina (MUSC) will be offered the opportunity to participate in the study. Those with valgus deformity greater than 10 degrees on plain radiographs will be excluded from the study. Participants will be reflective of the population of TKA candidates at MUSC, and will include adults over the age of 18 of both genders and all races. Consenting patients will all receive spinal anesthetic, and will be randomized to one of three arms: 1) Continuous femoral nerve catheter plus single injection sciatic nerve block, 2) Adductor canal catheter plus selective tibial nerve block, and 3) Adductor canal catheter alone. Patients unable to receive spinal anesthetic will be excluded. All patients will receive a standardized multimodal pain regimen and early mobilization.

**Preoperative data** will include basic demographics, visual analog pain scale (VAS) score, range of motion, body mass index (BMI), primary insurer, coronal angular deformity, and baseline opioid use. Surgical data will include tourniquet time and implant type. Time spent in pre-operative holding area, the operating room, and the post-anesthesia recovery unit will be recorded. SF-12, Patient Reported Outcomes Measurement Information System (PROMIS), and Knee Injury and Osteoarthritis Outcome Score (KOOS) will be collected as part of our participation in the Function and Outcomes Research for Comparative Effectiveness in Total Joint Replacement (FORCE-TJR).

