The primary outcome measure will be postoperative visual analog pain scale (VAS) score area under the curve (AUC) for 48 hours, recorded every six hours. Pain will be measured indirectly via total in-hospital opioid consumption. Functional outcome measures will be administered by members of the physical and occupational therapy team, who typically evaluate and treat patients once on the day of surgery and twice daily each day thereafter. They will document the patient's ability to perform independent terminal knee extension and grade knee buckling with ambulation on a scale of 0-2 during each encounter. Additionally, in the morning of postoperative day #1, a Katz Index of Independence in Activities of Daily Living score will be calculated. On the morning of postoperative day #2, the therapist will document distance walked by the patient, passive range of motion (flexion and extension), a timed up-and-go test (TUG), and calculate the AM-PAC (Activity Measure for Post-Acute Care) score. Patient reported outcome measures, specifically SF-12, PROMIS, and KOOS will be collected at 6 weeks and 3 months postoperatively. These time points are not included in the FORCE-TJR registry, and therefore will be independently collected and stored. Postoperative complications will be recorded. Finally, a brief survey will be administered at 3 months, presenting inquiries regarding satisfaction with the hospital stay, pain control, mobility, and the overall TKA experience. These inquiries will pose each question with a 0-10 scale, and respondents will be asked to select the number that corresponds to their level of satisfaction with each domain of their experience.

Data will be collected primarily by our study coordinator, but also by the PI. RedCap will be used to compile and store data. Collected data will be stored in a password-protected, MUSC network drive. Individual patient data will be linked to medical record number, but no other personal identifiers. These data and patient identifiers will only be accessible by study investigators. Most of the data collected are already part of the standard clinical care for total knee replacement patients, and are therefore already routinely available within the electronic medical record.

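### Does a power claim for a VAS difference of 2 fail to cover a primary outcome that is a 48-hour AUC?

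*Protocol*

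**What the plan says.** Section D of the Protocol defines the primary outcome: "The primary outcome measure will be postoperative visual analog pain scale (VAS) score area under the curve (AUC) for 48 hours, recorded every six hours". Section E.1.b repeats it.

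Later in Section D comes the only power claim tied to a treatment difference: "Preliminary estimates suggest the study will be adequately powered to detect a significant VAS difference of 2 at 25 subjects per group". It does not say whether the 2 points apply at one reading, as an average, or in some other form. It gives no SD, alpha or power level. The next sentence warns that real differences may be much smaller and could need a very large trial. The same paragraph describes the hypothesis testing as preliminary, gives a precision of 0.4 SD for a mean, and says of the treatment comparisons: "Effect sizes will then be estimated from the GLMMs in a pairwise manner".

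The arms are, first, "Continuous femoral nerve catheter plus single injection sciatic nerve block"; second and third, "Adductor canal catheter plus selective tibial nerve block, and 3) Adductor canal catheter alone". No expected duration of any block effect or pain difference is given.

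Section A also speaks of adequate power, but for a different purpose: to "establish estimates of variance that will help refine subsequent power analyses".

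**The concern.** A difference in VAS points and a difference in area under a VAS curve are in different units, and the Protocol does not connect them. If the 2 points were meant for a single reading, such as the worst early pain, the effect on the AUC could be far smaller.

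The arms make this plausible. Two of them share the adductor canal catheter and differ only by a tibial block, and the sciatic block in the remaining arm is a single injection. An early gap might fade well before 48 hours. Since Section A wants the pilot to inform later power calculations, a reader who took 2 points at 25 per group into an AUC-based trial could plan one that is too small.

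**Working it through.** **Inputs.** From Section D: 25 per group, a difference of 2, readings every 6 hours for 48 hours. Assumed, because the Protocol gives none of them: two-sided alpha 0.05, 80% power, one unadjusted pairwise comparison, a 0–10 scale, SD per reading of 2.0 to 3.0, equal correlation ρ between readings of 0.3 to 0.7, and nine readings (0, 6, …, 48 h).

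**1. The Protocol's figures.** The 25 per group cannot be reproduced without an SD, so solve for the SD it implies. By the normal approximation the detectable difference is (1.960 + 0.842) × √(2/25) = 0.79 SD. By noncentral t it is 0.809 SD. Two points is therefore detectable if the SD is at most 2/0.809 = 2.47. The stated precision does reproduce for one arm: 1.96/√25 = 0.39 SD, or 0.41 SD by t.

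**2. What the AUC requires.** Trapezoid weights are 3, 6 (seven times) and 3 hours, which sum to 48. The gap in AUC/48 for several shapes is:

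| Gap between arms | VAS-hours | AUC/48 |
|---|---|---|
| 2 throughout | 96 | 2.0 |
| falling linearly from 4 to 0 | 96 | 2.0 |
| 4 before 24 h, 2 at 24 h, 0 after | 96 | 2.0 |
| 2 through the 24 h reading, then 0 | 54 | 1.125 |
| 2 before the 24 h reading, then 0 | 42 | 0.875 |

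The condition is an average of 2 points over 48 hours. A gap need not last the full period to meet it.

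**3. SD of the 48-hour mean.** The squared weights (as fractions of 48) sum to 2 × (3/48)² + 7 × (6/48)² = 0.1172. So SD of AUC/48 = SD × √(ρ + (1 − ρ) × 0.1172). At SD 2.5 and ρ = 0.3 / 0.5 / 0.7 this is 1.545 / 1.868 / 2.144, all below 2.47. Under equal SD and equal correlation, the 48-hour mean is never more variable than one reading.

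**4. Power at 25 per group for an average gap of 2 points** (noncentral t):

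| SD per reading | ρ = 0.3 | ρ = 0.5 | ρ = 0.7 |
|---|---|---|---|
| 2.5 | 99% | 96% | 90% |
| 3.0 | 96% | 87% | 77% |

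On this reading the claim holds comfortably at SD 2.5. It falls just short of 80% only in the noisiest case shown.

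**5. The unfavourable case.** Suppose a 2-point gap lasts exactly 24 hours and counts as 2 × 24/48 = 1.0 point. At SD 2.5, power is 61% / 46% / 37%, and 80% power needs 39 / 56 / 74 per group. These numbers move a good deal with how the end of the gap meets the six-hourly readings: 31 / 45 / 58 per group at 1.125 points, 50 / 73 / 96 at 0.875. All of them follow from the 24 hours, which is an assumption.

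**The case for a change.** The strongest case for a change is that the Protocol chose to state a power claim, so its effect size should be in the units of the primary outcome. This is not a detail left for an analysis plan. The inputs are missing, the 25 per group cannot be rederived, and the arms give some reason to expect a gap that fades. Stating the scale and the SD would cost one sentence.

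Part of this stands: the scale of the 2 points is not stated, and if it meant a single reading, the claim would not carry over to the AUC. But the text does not say that it does. Reading it as a time average is natural, because AUC/48 is in VAS points. The arms do not settle the duration either. The femoral arm also differs from the other two in its continuous catheter, so a lasting difference is not excluded.

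The feared misuse is also guarded against. The sentence after the claim warns of subtler effects and much larger samples, and the later trial is to be designed from the pilot's estimated effect sizes and variances, not from this sentence.

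**Conclusion.** The concern does not call for a change. The Protocol leaves the scale of its 2-point difference and the SD behind it unstated, and a clarifying phrase would be harmless. But no stated number is shown to be wrong. Read as a difference in 48-hour mean VAS, the claim fits the primary outcome if the SD of that mean is about 2.47 or less. With 2.5 per reading, power is 90% to 99%.

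The need for 39 to 74 per group arises only if a gap of 2 points is assumed to stop at 24 hours, which no section supports. Writing the scale down would alter neither the sample size, the primary outcome, the model nor the conclusions of a pilot whose tests are declared preliminary.

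This rests on two-sided 0.05, 80% power, one unadjusted pair, and equal SDs and correlations across readings. None of these comes from the Protocol.

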### 3. POTENTIAL BENEFITS OF THE PROPOSED RESEARCH TO THE SUBJECTS AND OTHERS

As it is unclear which of the three research arms may be superior, direct benefit to participating patients cannot be guaranteed. The results of this study are expected to inform design of a subsequent larger randomized comparative effectiveness trial that will be adequately powered to prove clinically meaningful differences between treatments. Ultimately, knowledge gained from this project will provide clinicians the ability to choose the most optimal treatment option for TKR patients, and therefore benefit future patients.

Current literature suggests equivalent risks among the three proposed treatment arms. The remaining risks inherent with major surgery, and TKR specifically, are not expected to be affected by randomization. All proposed treatments are currently available and in use for TKR patients at MUSC.

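### Does the pilot promise clinically meaningful differences that 25 patients per arm cannot support?

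*Protocol*

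**What the plan says.** The Protocol, Section D, closes its description of the pilot with the expectation that the team will "define clinically meaningful though perhaps not statistically significant differences in efficacy, safety, patient-reported and objective outcomes". Section E.4 repeats this word for word. Section A has a looser version: "we do expect to produce clinically meaningful, if not statistically significant findings".

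Three other statements bear on it:

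- **Power.** Section D describes the study as "adequately powered to detect a significant VAS difference of 2 at 25 subjects per group". It gives no SD, power level or significance level. It adds at once that the true differences may be considerably smaller and could need a very large trial.
- **Precision and use.** Section D states the precision of the means, "with 95% confidence intervals extending just 0.4 standard deviation units in either direction". On the treatment contrasts it says: "Effect sizes will then be estimated from the GLMMs in a pairwise manner". The stated purpose of those effect sizes is to help design a larger, more definitive trial. The hypothesis tests and the effect estimates are both called preliminary.
- **Proof.** Section E.3 assigns it to a later "trial that will be adequately powered to prove clinically meaningful differences between treatments".

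**The concern.** A difference that is not significant at the two-sided 5% level has a 95% interval that includes zero. The data then do not settle even its direction, so it seems wrong to announce in advance that such a difference will be clinically meaningful. Section E.3 appears to concede this by leaving proof to the next trial.

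The power statement seems to sharpen the point. If the pilot really is adequately powered for 2 VAS points, an observed difference of 2 would be significant. Every non-significant VAS difference would then fall below the only difference the protocol names.

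At stake is what the pilot reports. Many outcomes are compared across three pairs of arms, so chance alone will produce some sizeable non-significant differences. If these were presented as meaningful, they could colour the funding application and the design of the next trial.

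**Working it through.** **Inputs.** 75 patients in three arms, 25 per group, 95% intervals and a VAS difference of 2, all from Section D. Assumed: equal allocation (implied by 25 per group and 75 in total), a two-sided 5% level, no multiplicity adjustment and no baseline adjustment.

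**1. The protocol's own figure.** The half-width for one arm mean is 1.96/√25 = 0.392 SD, or 2.064/√25 = 0.413 SD with t on 24 df. Both round to the stated 0.4 SD, which is correct for an arm mean.

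**2. Half-width for a difference between two arms.** Critical value × √(2/25), where √(2/25) = 0.2828:

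| Critical value | Half-width |
|---|---|
| 1.960 (normal) | 0.554 SD |
| 1.993 (t, 72 df) | 0.564 SD |
| 2.011 (t, 48 df) | 0.569 SD |

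So an unadjusted non-significant difference is smaller than about 0.57 SD. This part of the concern is right.

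**3. Can a real difference be non-significant here?** Noncentral t, two-sided 5%, 25 against 25:

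| True difference | Power | Non-significant |
|---|---|---|
| 0.3 SD | 18% | 82% |
| 0.4 SD | 28% | 72% |
| 0.5 SD | 41% | 59% |

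If a difference of this order matters to patients, the likeliest single result is that it exists and is not significant. The protocol's phrase describes that situation. An interval of ±0.57 SD that includes zero does not establish a meaningful effect, but it does not exclude one either.

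**4. The link to the 2-point VAS difference.** The SD is not given, so it has to be worked back from an assumed power. A difference of 2 at 25 per group has 80% power if the SD is 2.47 and 90% if it is 2.14. The smallest significant observed difference is 0.569 × SD, about 1.41 and 1.22 points respectively. Non-significant VAS differences do then lie below 2. That would be a contradiction only if 2 were the smallest difference that matters. Section D gives 2 as a detectable difference and nowhere as a threshold of clinical importance. The disputed sentence also covers safety, patient-reported and objective outcomes, for which no power is claimed.

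**5. How often chance produces such differences.** In 400,000 simulated pilots with three identical arms of 25 and one outcome, at least one pair showed a non-significant difference of 0.3, 0.4 or 0.5 SD or more in 51%, 28% and 9% of pilots. Section D lists roughly 20 outcomes if time points are counted and each instrument yields one score, so about 20 × 3 = 60 pairwise contrasts. The expected numbers that are non-significant yet reach those thresholds are 60 × 0.242 = 14.5, 60 × 0.112 = 6.7 and 60 × 0.031 = 1.9. The calculation is correct, but the thresholds are assumed, the outcome count is one possible count, and binary and ordinal outcomes are treated as standardized means. It describes any three-arm pilot of this size and would be the same if the sentence were deleted.

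**6. The passages side by side.** Section D and Section E.4 say that meaningful differences may fail to reach significance. Section E.3 says a larger trial will be powered to prove them. These agree: a study that expects not to reach significance leaves proof to its successor. Section A speaks of findings rather than treatment differences, and its next sentence is about estimating variances for later power calculations.

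**The case for a change.** The strongest argument for the concern is grammatical. In the disputed sentence the hedge attaches to significance, and nothing qualifies the claim of clinical meaning. The verb suggests that meaningful differences will be established, while no threshold of importance is given for any outcome. The statement appears in three places and stands close to the funding plans, where a reader could take it at face value. Calling the study a pilot does not remove this, because the word preliminary is applied to the tests and estimates and not to this sentence.

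Some of that stands. The verb is loose, and speaking of estimating differences would be clearer. The chance counts are a fair reminder of how unadjusted contrasts from a small pilot should be read.

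It does not amount to an error in the plan. The sentence opens as an expectation and governs no analysis. Thresholds of importance and rules for interpretation commonly belong in the statistical analysis plan, which is not shown, so their absence here is no fault. The natural remedy, allowing the words clinically meaningful only where the interval excludes zero, is itself disputable. It ties clinical relevance to significance, yet would let through the 60 × 0.05 = 3 contrasts expected to be significant by chance. Applied to safety, it would sit awkwardly with Section E.2.b, which lets investigators act on a trend in adverse events without any test.

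**Conclusion.** The concern does not hold. Its central figure is correct: a half-width of 0.55 to 0.57 SD for an unadjusted difference between two arms of 25, against the protocol's correct 0.4 SD for a single mean. But no stated figure, rule or threshold in the protocol is wrong, and Sections A, D, E.3 and E.4 can be read together without contradiction. The disputed sentence is a hedged expectation, and Section D already calls the results preliminary and intends them for designing the next trial. Following the protocol as written gives the same sample size, the same pairwise contrasts and the same intervals with or without it. What remains is a preference about wording.

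This rests on a two-sided 5% level, equal arms of 25 and no multiplicity adjustment. Adjusting for three comparisons would widen the half-width to about 0.68 to 0.69 SD, and adjusting for a baseline correlated 0.3 to 0.6 with the outcome (assumed) would narrow it to 0.54 to 0.45 SD. Neither changes the conclusion. It would be different if the protocol named 2 VAS points as the smallest important difference, or made the label a reporting rule. It does neither.
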